4.2.4. Additional estimands

The following supplementary estimands are defined to support the primary objective.

4.2.4.1. Using Hypothetical Strategy to Deal with ICE of Discontinuation of, Interruption of, and Adherence to IP

The first supplementary estimand is defined in the same way as the primary estimand, except the intercurrent event of discontinuation of, interruption of, and adherence to IP will be handled assuming they had not happened (hypothetical strategy). Discontinuation of GSK3228836 or significant interruption/non-adherence to GSK3228836 will be handled assuming the intercurrent event had not happened (hypothetical strategy). Significant interruption/non-adherence is defined as a gap of >=21 days between treatment doses at any time during the on-treatment period. According the hypothetical strategy, any data collected after the intercurrent event will be set to missing.

This supplementary estimand supporting the primary objective in participants with CHB on stable nucloes(t)ide therapy and participants with CHB not currently on nucleos(t)ide therapy is the proportion of participants in each treatment arm 1, 2, 3 and 4 who achieve SVR for 24 weeks after the planned end of GSK3228836 treatment in the absence of rescue medication, had they not been affected by discontinuation of IP, interruptions in IP, adherence to IP, or wide disruptive events.

4.2.4.2. Measuring SVR from Actual End of Treatment instead of Planned End of Treatment

The second supplementary estimand is defined in the same way as the primary estimand, except the assessment time frame for participants achieving SVR will be 24 weeks after the actual end of treatment. Therefore, the strategy for intercurrent events of treatment discontinuation will be while-on-treatment. This supplementary estimand supporting the primary objective in participants with CHB on stable nucleos(t)ide therapy and participants with CHB not currently on nucleos(t)ide therapy is the proportion of participants in each treatment arm 1, 2, 3 and 4 who achieve SVR for 24 weeks after the actual end of GSK3228836 treatment in the absence of rescue medication, regardless of completing IP, interruptions in IP or adherence to IP, had they not been affected by wide disruptive events.

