4.2.2.2. Intercurrent Events and Missing data

The intercurrent event of use of rescue medication has been incorporated into the definition of variable (composite strategy). The intercurrent event of discontinuation of, interruption of, and adherence to IP not due to wide disruptive event will be ignored (treatment policy).

To prevent the efficacy of GSK3228836 being penalized for uncontrollable and unusual events (i.e. wide disruptive events such as the COVID-19 pandemic), if a wide disruptive event leads to discontinuation of GSK3228836 or significant interruption/non-adherence to GSK3228836, this will be handled assuming the intercurrent event had not happened (hypothetical strategy). Significant interruption/non-adherence is defined as a gap of >=21 days between treatment doses at any time during the on-treatment period. According the hypothetical strategy, any data collected after the intercurrent event will be set to missing.

If all analysis windows have non-missing response information, a participant's response (Responder or Non-responder) is determined as follows:

- 1. If rescue medication was used, then the participant is a non-responder.
- 2. If HBsAg <LLOQ and HBV DNA <LLOQ in each of the analysis window, then the participant is a Responder, otherwise the participant is non-responder. Note: A result of TND is considered as <LLOQ.

The following approach will be used to determine a participant's response when HBsAg and HBV DNA data are missing from visits required to derive the primary endpoint:

For participants where wide disruptive events (such as COVID-19 pandemic) prevent assessment of the primary outcome, SVR will be imputed using all available data for

participants for whom SVR can be assessed. The final inference from the hierarchical Bayesian model will account for the missing data assuming MAR. For other participants where SVR in the absence of rescue medication cannot be ascertained due to missing data (withdrawal from the study or missing due to other reasons, but not due to a wide disruptive event), the participant will be assumed not to have achieved SVR (non-responder imputation).

After the imputation above, if there is missing data in at least one analysis window then the participant is a non-responder.

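### SAP 4.2.4.1 gives no imputation rule for the data it sets to missing, and the inherited rules would score participants who stop or interrupt for ordinary reasons as failures, against the estimand's hypothetical target

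*SAP*

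**What the plan says.** **SAP 4.2.4.1.** "The first supplementary estimand is defined in the same way as the primary estimand", apart from a hypothetical strategy for discontinuation, interruption and non-adherence. There are two triggers. One is discontinuation; the other is a dose gap: "Significant interruption/non-adherence is defined as a gap of >=21 days between treatment doses at any time during the on-treatment period". After either, "any data collected after the intercurrent event will be set to missing". The target is SVR in arms 1 to 4 "had they not been affected by discontinuation of IP, interruptions in IP, adherence to IP, or wide disruptive events". No imputation rule follows.

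**SAP 4.2.2.2** holds the missing-data rules of the primary estimand, in three parts:

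- Wide disruptive events: "For participants where wide disruptive events (such as COVID-19 pandemic) prevent assessment of the primary outcome, SVR will be imputed using all available data" from participants whose SVR can be assessed, and "The final inference from the hierarchical Bayesian model will account for the missing data assuming MAR".
- Everything else is scored as failure: "the participant will be assumed not to have achieved SVR (non-responder imputation"). The scope of this second rule is given as "withdrawal from the study or missing due to other reasons, but not due to a wide disruptive event".
- A closing rule: a participant who still lacks a value in one or more windows after that imputation is a non-responder.

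**SAP 4.2.3** adds a MAR sensitivity analysis, for the primary estimand only.

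Nothing else settles the point. Protocol 9.4.2.3 makes the same split between wide disruptive events and other causes. Protocol 9.4.2.2 describes only the estimand timed from actual end of treatment. Table 9 in SAP 4.8 does not mention 4.2.4.1.

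**The concern.** A hypothetical strategy deletes what happened after the event so that the outcome without the event can be estimated. Here the deletion is specified and the estimation is not. The inherited rule whose wording covers an ordinary discontinuation (an adverse event, a participant's choice) is non-responder imputation. A programmer who follows the text would delete observed results and then count the deletion as failure. That is a composite-failure analysis carrying a hypothetical label.

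The likely misreading is about direction. A reader expects this estimand to show what uninterrupted treatment could achieve. If it comes out equal to or below the treatment-policy result, the reader may conclude that staying on treatment adds nothing, when the ordering was forced by the scoring.

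The responders lost this way need not be few. Protocol 7.1.1 (Table 6) provides for dose holds on ALT elevation, and Protocol 8.3.7.1 says therapeutic ALT flares correlate with antiviral effect. In the earlier study summarised in Protocol Table 5, 6 of 8 participants with flares had an HBsAg reduction above 1 log. Gaps that reach 21 days could therefore fall on participants likely to respond.

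**Working it through.** **1. The nearest printed figure.** The SAP gives no number for this estimand, so I checked the calculation against SAP Table 11. With a Beta(0.5, 0.5) prior and n = 66, the smallest number of responders r with Pr(rate > 20%) > 75% is 16. At a true rate of 30%, P(X ≥ 16) for X ~ Binomial(66, 0.30) is 87.7%; the SAP prints 88%. It reproduces.

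**2. Which rule applies to whom.**

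| Event | Data afterwards | Rule in 4.2.2.2 that fits | Outcome as written |
|---|---|---|---|
| Stop or gap due to a wide disruptive event | set to missing | MAR | imputed |
| Stop for any other reason | set to missing | other reasons, then closing rule | non-responder |
| Gap of 21 days or more for any other reason | set to missing | other reasons, then closing rule | non-responder |

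By SAP Tables 2 and 3 the first post-treatment window opens on Day 183 (arms 1, 2 and 4) or Day 99 (arm 3). An early stop of GSK3228836, or a qualifying gap during it, comes before those windows. All three post-treatment windows are then empty, so rows 2 and 3 always end in failure.

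**3. Ordering against the primary estimate.** Leave aside participants imputed under MAR. Let N be the arm size, R the SVRs among unaffected participants, and S the SVRs observed among affected participants.

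- Primary (treatment policy): (R + S)/N
- First supplementary estimand as written: R/N
- Difference: S/N, which is zero or positive

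Illustration: N = 66, 7 affected, 18 of the other 59 reach SVR.

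| S | Primary | As written | MAR, approximately |
|---|---|---|---|
| 0 | 18/66 = 27.3% | 18/66 = 27.3% | 18/59 = 30.5% |
| 1 | 19/66 = 28.8% | 27.3% | 30.5% |
| 2 | 20/66 = 30.3% | 27.3% | 30.5% |

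**4. Size over a range.** Let d be the fraction affected for reasons other than a wide disruptive event, and p the SVR rate in the others. As written the estimate is p(1 − d). Under MAR it targets p, ignoring differences in stratum mix. The documents give no value for d, so the range is an assumption.

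| d | p = 20% | p = 30% | P(≥ 16 of 66), p = 30% |
|---|---|---|---|
| 0% | 20.0% | 30.0% | 87.7% |
| 5% | 19.0% | 28.5% | 81.6% |
| 10% | 18.0% | 27.0% | 73.6% |
| 15% | 17.0% | 25.5% | 63.9% |
| 20% | 16.0% | 24.0% | 52.9% |

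The last column shows scale only. The SAP attaches no decision criterion to this estimand.

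**The case against.** The best reply is that MAR is implied. SAP 4.2.4.1 repeats the hypothetical-strategy text of 4.2.2.2 almost unchanged, including the 21-day definition and the set-to-missing sentence, and in 4.2.2.2 that device goes with MAR. Since 4.2.4.1 departs from the primary estimand precisely in how this event is handled, the whole treatment may have been meant to carry over. This is a plausible account of intent. It does not stand as a reading of the rules, because 4.2.2.2 confines MAR to wide disruptive events and assigns other causes to non-response. To infer MAR is to override that wording.

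A second reply is that MAR suits a pandemic better than a safety stop. Events linked to ALT may be related to response, and the model adjusts only for the HBsAg and HBeAg strata. That stands as a caution: MAR is an assumption, and another stated model-based method could be defended. It does not defend non-response scoring.

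Third, this is one of four supplementary estimands in a study that estimates without hypothesis testing. That limits the weight of the point.

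A reader might also infer three stronger things that the documents do not support:

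- That non-responder imputation is the only stated rule. MAR is stated for wide disruptive events, and in 4.2.3 for a primary sensitivity analysis.
- That every discontinuer is scored a failure. Those who stop because of a wide disruptive event are imputed.
- That the result must lie below the primary. With S = 0 the two are equal.

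**Conclusion.** The missing rule is certain. The failure scoring is what the inherited wording yields when applied literally; it is not a rule written for this estimand. On that wording the analysis does not estimate its declared target.

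Outside MAR-imputed participants, the shortfall against the primary estimate is the share of the arm observed to reach SVR after a qualifying stop or gap. The shortfall against MAR is p × d: 1 to 4 percentage points at p = 20% for d from 5 to 20%, and 1.5 to 6 points at p = 30%. These sizes rest on assumed values of d and on affected participants responding like the others in their stratum had the event not occurred.

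The primary analysis is unaffected, and no stated decision depends on this estimand. The correction is still worth making, because the result would be reported under a label it does not fit.

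**What to change.** Add to SAP 4.2.4.1:

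- Data set to missing under this strategy are handled under MAR in the hierarchical model, as 4.2.2.2 does for wide disruptive events.
- Non-responder imputation and the closing rule on empty windows apply only to other missing data. Without this limit the closing rule could still turn these participants into failures.
- Participants who were already non-responders before the event, for example through rescue use, remain non-responders.

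Also use one term for the triggering treatment. The section speaks of IP in one sentence and GSK3228836 in the next. In arm 3 the injections after Week 12 are placebo, so stopping them is a discontinuation under one term and not under the other, and the post-treatment data would be deleted or kept accordingly.

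The cost is a few sentences in the SAP and a matching change to the derivation program for this estimand. It needs no new data and no change to the primary analysis.

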4.2.4.3. Using Principal Stratum Strategy to Deal with Protocol Deviations

The third supplementary estimand is defined in the same way as the primary estimand, except for the population, variable and intercurrent events definitions. The population is participants with CHB not currently on nucleos(t)ide therapy. The variable for this estimand will be defined as sustained virologic response (SVR) for 24 weeks after the planned end of GSK3228836 treatment in the absence of rescue medication for medical reasons. The intercurrent event of use of rescue medication will be separated into two:

- 1. Use of rescue medication for medical reasons
- 2. Use of rescue medication because of a protocol deviation

The use of rescue medication for medical reasons has been incorporated into the definition of variable (composite strategy). The use of rescue medication because of a protocol deviation will be handled by excluding these participants from the analysis (principal stratum strategy). This supplementary estimand supporting the primary objective in participants with CHB not currently on nucleos(t)ide therapy is the proportion of participants in each treatment arm 1, 2, 3 and 4 who achieve SVR for 24 weeks after the planned end of GSK3228836 treatment in the stratum of participants who did not use rescue medication in error, in the absence of rescue medication for medical reasons, regardless of completing IP, interruptions in IP or adherence to IP, had they not been affected by wide disruptive events.

4.2.4.4. Using a Modified Definition of SVR

The fourth supplementary estimand is defined in the same way as the primary estimand, except the variable is defined using a modified definition of sustained virologic response (SVR) for 24 weeks after the planned end of GSK3228836 treatment in the absence of rescue medication. The modified definition of sustained virologic response is defined as

observing HBsAg <LLOQ and HBV DNA <LLOQ at each analysis window in the 24 weeks after the end of GSK3228836 treatment. Any observation of HBsAg ≥LLOQ or HBV DNA ≥LLOQ must be confirmed at a consecutive visit (including unscheduled visits) for the patient to be classed as having lost their SVR.

Subjects who have a value of HBsAg ≥LLOQ or HBV DNA ≥LLOQ at their last visit, which cannot be confirmed due to no further follow up, will be treated as non-responders.

This supplementary estimand supporting the primary objective in participants with CHB on stable nucloes(t)ide therapy and participants with CHB not currently on nucleos(t)ide therapy is the proportion of participants in each treatment arm 1, 2, 3 and 4 who achieve the modified definition of SVR for 24 weeks after the planned end of GSK3228836 treatment in the absence of rescue medication, regardless of completing IP, interruptions in IP or adherence to IP, had they not been affected by wide disruptive events.

4.3. Secondary Endpoint(s) Analyses

4.3.1. Key secondary endpoint(s)

4.3.1.1. Efficacy of GSK3228836 on biomarkers and virus-specific antibody response

The group of estimands supporting the secondary objective of assessing the efficacy of GSK3228836 on biomarkers and virus-specific antibody responses for each sub-population are the population summary for each variable in each treatment arm 1-4.

Missing data for variables defined above (except for Time to ALT normalization) will be ignored, only available data will be summarized. No sensitivity analysis is planned for the group of estimands supporting this objective.

Estimands supporting this objective are defined as follows:

- **Population**: one subpopulation of participants with CHB on stable nucleos(t)ide therapy and a second subpopulation of participants with CHB not currently on nucleos(t)ide therapy. For the time to ALT normalization endpoint, only subjects with ALT>ULN at baseline will be included. For summaries of HBe antibody (anti-HBeAg) levels, only participants who are HBeAg Positive at baseline will be included.
- Treatments: arms 1-4. Estimation within each arm.
- Intercurrent events: For the proportion of participants achieving HBsAg <LLOQ and HBV DNA <LLOQ in the absence of rescue medication at the end of treatment analysis window, end of treatment will be determined using the end of treatment analysis window defined in Section 4.2.2. In line with the primary endpoint, missing data not due to wide disruptive events will be imputed as non-response. Missing data due to wide disruptive events will be ignored without any imputation.

Other endpoints will be summarized regardless of completing IP, interruptions in IP or adherence to IP (treatment policy strategy) and regardless of rescue medication (except

for ALT normalization which can only be achieved in the absence of rescue medication). HBV DNA, HBsAg, HBeAg levels that are below the LLOQ will be imputed for summaries of actual values and change from baseline following the rules in Section 4.1.1.

1) Categorical Variables:

- Achieving HBsAg <LLOQ and HBV DNA <LLOQ at the end of treatment analysis window. Data will be presented overall and by baseline stratification factors (HBsAg <3 log IU/mL and Negative HBeAg; BsAg >3 log IU/mL and Negative HBeAg; HBsAg <3 log IU/mL and Positive HBeAg; HBsAg >3 log IU/mL and Positive HBeAg; HBsAg <3 log IU/mL and All HBeAg; All HBsAg and Negative HBeAg; HBsAg <3 log IU/mL and All HBeAg; All HBsAg and Positive HBeAg)
- Categorical changes from baseline in HBsAg (e.g., <0.5, ≥0.5, ≥1, ≥1.5, ≥3 log₁₀ IU/mL) and in HBV DNA (e.g., <1, ≥1, ≥2, ≥3 log IU/mL). Change from baseline will be presented at each visit and for the following time periods: up to and including Week 6, Up to and including Week 12, Up to and including Week 24, Up to and including off-treatment Week 24. Data will be presented overall and by baseline stratification factors (HBsAg <3 log IU/mL and Negative HBeAg; BsAg >3 log IU/mL and Negative HBeAg; HBsAg >3 log IU/mL and Positive HBeAg; HBsAg >3 log IU/mL and All HBeAg; All HBsAg and Negative HBeAg; HBsAg <3 log IU/mL and All HBeAg; All HBsAg and Positive HBeAg)
- ALT normalization (ALT \leq ULN) over time in absence of rescue medication in participants with baseline ALT \rightarrow ULN
- HBe antibody (anti-HBeAg) levels in HBeAg Positive patients
- HBs antibody (anti-HBsAg) levels (HBs Antibody >=11.5 IU/L is HBs antibody positive and HBs Antibody <11.5 IU/L is HBs antibody negative)
- **Population summary:** proportion of participants in each category for each treatment arm.

2) Continuous Variables:

- Actual values and change from baseline over time of HBsAg and HBV DNA
- Actual values and change from baseline of HBeAg levels
- HBs antibody (anti-HBsAg) levels
- **Population summary**: mean values and mean changes from baseline for each variable in each treatment arm.

3) Time to Event Variable:

- Time to ALT normalization in absence of rescue medication in participants with baseline ALT>ULN.
- **Population summary**: Turnbull's estimator for the non-parametric estimation of time to ALT normalization in each treatment arm.

ALT normalization is defined in subjects with ALT>ULN at baseline as a return to ≤ULN (ULN = 40 for males and 33 in females). Time to ALT normalization is defined as time from baseline to the first follow-up where subject's ALT has returned to normal.

For participants who withdraw from the study or Participants with ALT>ULN at the end of study, time to ALT normalization will be censored at the time of last visit with non-missing ALT value available. Participants who receive rescue medication cannot go on to achieve the event of 'ALT normalization in the absence of rescue medication'; such participants will be censored at the end of the follow up period.

4.3.1.2. Comparison of efficacy between arms 1, 2 and 3

Definition of Estimands

Estimands supporting secondary objective of comparing the efficacy between arms 1, 2, and 3 are defined as follows:

- **Population**: separate assessment for the following:
 - participants with CHB on stable nucleos(t)ide therapy
 - participants with CHB not currently on nucleos(t)ide therapy
- Variable: Sustained virologic response (SVR) for 24 weeks after the end of GSK3228836 treatment in the absence of rescue medication.
- **Treatments**: arms 1, 2, and 3. Three treatment comparisons between: arms 1 and 2, arms 1 and 3, and arms 2 and 3.
- **Intercurrent events**: use of rescue medication, and discontinuation of/interruption of/adherence to IP. The use of rescue medication has been incorporated into the definition of variable (composite strategy). Discontinuation of, interruption of, and adherence to IP will be ignored (treatment policy). Wide disruptive events (such as COVID-19 pandemic) leading to discontinuation of, interruption of, and non-adherence to GSK3228836 will be handled assuming they had not happened (hypothetical strategy).
- **Population summary**: difference in proportion of participants who achieve SVR between treatment arms.

The group of estimands supporting this objective for each sub-population are the difference in each treatment comparisons in the proportion of participants who achieve SVR for 24 weeks after the end of GSK3228836 treatment in the absence of rescue medication regardless of completing IP, interruptions in IP or adherence to IP had they not been affected by wide disruptive events.

The non-responder imputation described in Section 4.2.2 will be used when HBsAg and HBV DNA data are missing from visits required to derive the endpoint.

Main analytical approach

Comparisons between arms will be made by calculating differences between the posterior distributions of the response rate in each arm which will be summarised to obtain posterior means and CIs. Samples from the posterior distribution of the response rates in each arm will also be used to obtain posterior probabilities of interest (e.g. Pr(Arm 1 - Arm 2 > -5% | Data)). The point estimates of differences in sustained virologic response rate with 95% credible intervals will be calculated for the treatment comparisons described in the estimands.

Posterior probability for the differences of following comparisons will also be reported;

- 1. Arm 1 vs. Arm 2
- 2. Arm 1 vs. Arm 3
- 3. Arm 2 vs. Arm 3

[figure not shown]
Regimen Selection Approach

If success criteria is met for more than one arm, regimen selection will be conducted. The non-inferiority (NI) decision rules for two-treatment comparison is Posterior Prob(less intensive arm SVR rate – more intensive arm SVR rate > -5%) > 65%. The arms are ordered in intensity from 1 (most intensive) to 4 (least intensive).

[figure not shown]
For each comparison, the posterior distribution of difference in SVR rate will be derived and the posterior probability (less intensive arm SVR rate - more intensive arm SVR rate > -5%) will be obtained based on the model described in Main analytical approach present under Section 4.3.1.2. If posterior probability is >65%, EoS NI rule is met.

If 2 arms meet the success rule, NI comparison between the 2 arms will be conducted. If the NI rule is met, then select the less intensive arm, otherwise select the more intensive arm.

If 3 arms meet the success rule, sequential two-treatment comparisons will be conducted for the 3 arms. The regimen selection follows the decision tree below.

If 4 arms meet the success rule, sequential two-treatment comparisons will be conducted for the 4 arms. The regimen selection follows the decision tree below.

Operating Characteristics for Regimen Selection

The Operating characteristics of regimen selection are summarized in Table 5 for a range of scenarios.

Table 5 Operating Characteristics for Regimen Selection

Arm 1 True rate	Arm 2 True rate	Arm 3 True rate	Arm 4 True rate	Prob of selecting arm 1	Prob of selecting arm 2	Prob of selecting arm 3	Prob of selecting arm 4	Prob of selecting none
30%	30%	30%	30%	16%	21%	28%	35%	0%
30%	30%	30%	25%	19%	26%	36%	19%	0%
30%	30%	25%	30%	21%	29%	11%	39%	0%
30%	25%	30%	30%	21%	7%	33%	39%	0%
25%	30%	30%	30%	4%	23%	33%	39%	0%
30%	30%	25%	25%	26%	37%	15%	22%	0%
30%	25%	30%	25%	26%	9%	43%	22%	0%
25%	30%	30%	25%	6%	30%	43%	22%	0%
30%	25%	25%	30%	30%	11%	14%	44%	1%
25%	30%	25%	30%	7%	34%	14%	44%	1%
25%	25%	30%	30%	7%	8%	40%	44%	1%
30%	25%	25%	25%	38%	15%	19%	26%	1%
25%	30%	25%	25%	9%	44%	19%	27%	1%
25%	25%	30%	25%	9%	11%	52%	27%	1%
25%	25%	25%	30%	11%	15%	19%	53%	2%

